2.5 Analysis of the primary objective

Primary analysis was conducted and the result was reported in "the Week 24 CSR" and not applicable in this document.

2.6 Analysis of the key secondary objective

Not Applicable.

2.7 Analysis of secondary efficacy objective(s)

Most secondary analyses were reported in "the Week 24 CSR" and not applicable in this document. The below analyses which were previously performed will be repeated with updated data for the final analysis.

Best response rate

The best response rate is defined as the proportion of patients achieving $\geq 35\%$ reduction in spleen volume from Baseline at any post-baseline assessment. The best response rate will be estimated with an associated 95% confidence interval based on the normal approximation.

Duration of maintenance of a greater or equal to 35% reduction from Baseline in spleen volume

For patients who had at least one $\geq 35\%$ reduction in spleen volume from Baseline at postbaseline, the duration of response will be calculated. The start date of the duration is defined as the first spleen volume measurement that is $\geq 35\%$ reduction from Baseline, and the end date of the response duration is defined as the earliest of the following:

- Death.
- $A \ge 25\%$ increase in spleen volume by MRI compared to Baseline.
- Splenic irradiation.

- Leukemic transformation as defined by a bone marrow or a peripheral blood blast count of $\geq 20\%$.
- Splenectomy.

In the event that a patient experiences leukemic transformation, requires therapy with splenic irradiation, or experiences a $\geq 25\%$ increase in spleen volume by MRI compared to Baseline, the study drug must be permanently discontinued. Therefore, the end date of the duration will be defined as the earliest date for one of the following for patient with any event of disease progression:

- Date of death.
- Assessment date of spleen volume with a \geq 25% increase compared to Baseline measured by MRI.
- Date of leukemic transformation captured on the e-CRF page "Leukemic transformation".
- Date of Splenic irradiation/Splenectomy captured on either the "Concomitant medications/Significant non-drug therapies" or "Antineoplastic therapies since discontinuation of study drug" e-CRF pages.

If a patient undergoes splenectomy, and the investigator believes that it is in the patient's best interest to continue treatment with INC424 due to symptomatic improvement, the patient may continue treatment assuming she/he has fully recovered from the splenectomy procedure within 12 weeks. Even if she/he continues therapy with INC424, the event will be assumed to have occurred for that patient. Note that the date of splenectomy will be recorded on the e - CRF page "Concomitant medications/Significant non-drug therapies" if that patient continues treatment with INC424.

The censoring date is defined as the date of the last adequate assessment of spleen volume for patients with no event of disease progression. Patients who had more than 1 consecutive missing spleen volume assessment will be censored at the last adequate assessment prior to the consecutive missing assessments, regardless of the occurrence of a subsequent death or any event of disease progression.

The duration of response will be evaluated using a Kaplan-Meier estimate. Note that the analysis will be performed only for patients who achieved a least one \geq 35% reduction in spleen volume at any time on study.

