6.2.4.1 Discontinuation criteria for disease progression

The following events are considered disease progression.

- A ≥25% increase in spleen volume by MRI compared to Baseline: the Investigator will be notified via the central reader
- Splenic irradiation
- Leukemic transformation as defined by a bone marrow or a peripheral blood blast count of $\geq 20\%$
- Splenectomy

Novartis	Confidential	Page 33
Oncology Clinical Trial Protocol		Protocol No. CINC424A2202

In the event that a patient experiences leukemic transformation, requires therapy with splenic irradiation, or experiences a \geq 25% increase in spleen volume by MRI compared to Baseline, study drug must be permanently discontinued. If a patient undergoes splenectomy, and the Investigator believes that it is in the patient's benefit to continue therapy with INC424 due to symptomatic improvement, the patient may continue therapy assuming s/he has fully recovered from the splenectomy procedure within 12 weeks.

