Urinalysis	D	7.2.2.6.3			Х			Х					Х				х

Novartis	
Oncology Clinical Trial Protoco	I

Confidential

Page 40 Protocol No. CINC424A2202

	Category	Reference to assessment types	Screening	Base	eline	Treatment Phase (± 7day Window) *Day1 has no time window **Only for Day14, ± 3 Day Window											
Visit Number			1	2	2	3	4	5	6	7	8	9	10	11	12	13	14
Дау			-42 to -8	-28 to -7	-7 to - 1	1*	14**	28	56	84	112	140	168	210	252	294	336
Week			-6 to -2	-4 to -2	-1	1	2	4	8	12	16	20	24	30	36	42	48
Concomitant medications	D	6.3.1	Х	Х	Х	Х	Х	Х	Х	Х	Х	Х	Х	Х	Х	Х	Х
Transfusion history/status	D	6.3.1	х	Х	Х	Х	Х	Х	х	х	Х	Х	Х	Х	Х	х	Х
Adverse events	D	7.2.2.1	Х	Х	Х	Х	Х	Х	Х	Х	Х	Х	Х	Х	Х	Х	Х
Dispense INC424	S	6.5.1				Х	Х	Х	Х	Х	Х	Х	Х	Х	Х	х	Х
INC424 morning dose at the study site	D	7.2.3.1				х	Х	х		х							
Drug accountability assessment	S	6.5.4.2					Х	Х	Х	Х	Х	Х	Х	Х	Х	Х	Х
INC424 dosing	D	6.1				Continuous											

Table 7-2Visit evaluation schedule (continued)

	Category	Reference to assessment types	INC424 dose increased or restarted (+/- 3 days)	Т	reatment Phase (+/- 7 days)	End of Treatment	Follow up (Study Evaluation Completion) (+10 days)
Visit Number			Extra	15, 17, 19, etc.	16, 18, 20, etc.	777	778
Day				378, 462, 546, and q12 weeks	420, 504, 588, and q12 weeks		30 days after End of Treatment
Week			2 and 4 weeks after dose increased or restarted	54, 66, 78, and q12 weeks	60, 72, 84, and q12 weeks ***only q24 weeks, e.g., 72, 96, 120 ****only q48 weeks, e.g., 96, 144, 192		
Weight	D	7.2.2.4			Х	Х	Х
Comprehensive physical examination	S	7.2.2.2			X***		Х
Targeted physical examination	S	7.2.2.2	Х	Х	Х	Х	
Measurement of spleen by palpation	D	7.2.1.2	Х	Х	Х	Х	Х
ECOG performance status	D	7.2.2.5	Х		Х	Х	
Vital signs	D	7.2.2.3	Х		Х	Х	Х
12-lead ECG	D	7.2.2.7.1			X***	Х	Х
Seven-day modified MFSAF v2.0 questionnaires	D	7.2.1.3			Х		
MRI of abdomen (or CT)	D	7.2.1.1			X***		

Novartis	
Oncology Clinical Trial Protoco	וכ

Confidential

	Category	Reference to assessment types	INC424 dose increased or restarted (+/- 3 days)	т	reatment Phase (+/- 7 days)	End of Treatment	Follow up (Study Evaluation Completion) (+10 days)
Visit Number			Extra	15, 17, 19, etc.	16, 18, 20, etc.	777	778
Day				378, 462, 546, and q12 weeks	420, 504, 588, and q12 weeks		30 days after End of Treatment
Week			2 and 4 weeks after dose increased or restarted	54, 66, 78, and q12 weeks	60, 72, 84, and q12 weeks ***only q24 weeks, e.g., 72, 96, 120 ****only q48 weeks, e.g., 96, 144, 192		

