7.2 Assessment types

7.2.1 Efficacy assessments

7.2.1.1 Imaging

The primary measure of spleen size will be by MRI. MRI of the abdomen will be performed at Baseline, and at visits corresponding to Weeks 12, 24, 36, 48 and every 24 weeks thereafter for all patients on study. MRI will be performed with a body coil because the objective is to measure organ volume, not to find very small lesions. MRIs will be performed by local radiologists who will be instructed not to provide a quantitative measure of spleen volume, but may provide a qualitative assessment such as enlarged, smaller, larger, etc. However, should a quantitative result be provided to the Investigator, this will not be considered a protocol violation, and the patient will still be evaluable. The scans from an individual patient will be read by a central reader upon transfer from the site radiologist. Spleen volume will be obtained by outlining the circumference of the organ and determining the volume using the validated technique of least squares. The MRI will not determine spleen length below the costal margin, as there are no validated approaches for determining this measurement. When a post-treatment assessment indicates that a patient has experienced $a \ge 25\%$ increase in spleen volume compared to Baseline, the Investigator will be notified from a central reader. MRI is the preferred method for obtaining spleen volume data. However, CT scans may be performed if the patient is not a candidate for MRI (because of the presence of metal clips in the body, or because of claustrophobia, for example). CT scans will be similarly processed by the same central laboratory as used for MRIs. Both for MRI and CT, procedure specific trainings for scanning and image capture will be provided by the Vendor. Generally, the same method (MRI or CT) should be used for all visits for a given patient unless a new contraindication to the use of MRI (i.e., pacemaker insertion) occurs. Please contact the Sponsor if a modality change is required.

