10.5.3 Best response rate

The best response rate is defined as the proportion of patients achieving \geq 35% reduction in spleen volume from Baseline at any post-baseline assessment. The best response rate will be estimated with 95% confidence interval.

10.5.4 Duration of maintenance of a greater or equal 35% reduction from Baseline in spleen volume

For patients who had at least one $\geq 35\%$ reduction in spleen volume from Baseline at postbaseline, the duration of response will be calculated. The start date of the duration is defined as the first spleen volume measurement that is $\geq 35\%$ reduction from Baseline, and the end date is defined as the earliest of the following:

- Death
- Any protocol-defined event of disease progression (see Section 6.2.4.1)

Censoring date is defined as the date of the last adequate assessment of the spleen volume. Patients who had more than 1 consecutive missing spleen volume assessment will be censored at the last adequate assessment prior to the consecutive missing assessments, regardless of the occurrence of a subsequent death or any event of disease progression.

The duration of response will be evaluated using a Kaplan-Meier estimate. Note that the analysis will be performed only for patients who achieved a \geq 35% reduction in spleen volume.

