1.2 Study objectives and endpoints

Table 1-1 shows objectives and endpoints for this study.

	· ·	
	Objective	Endpoint
Primary	To determine the efficacy of INC424 as assessed by reduction in spleen volume	Proportion of patients achieving ≥35% reduction in spleen volume from Baseline to Week 24 as measured by MRI (or CT scan in applicable patients)
Secondary	To determine the safety and tolerability of INC424	Safety and tolerability will be assessed by monitoring the frequency, duration and severity of adverse events, performing physical exams, and evaluating changes in vital signs, electrocardiograms (ECGs), serum chemistry, hematology and urinalysis results. Toxicity will be assessed using the Common Terminology Criteria for Adverse Events (CTCAE) v4.03.
Secondary	To evaluate the effects of INC424 on patient reported outcomes	Change in EORTC QLQ-C30 score from Baseline to Week 24.
		Change in total symptom score from Baseline to Week 24, as assessed by

 Table 1-1
 Objectives and endpoints

Novartis	
SAP	

		Endpoint
		Seven-day modified MFSAF v2.0
Secondary	To evaluate the duration of response as assessed by reduction in spleen volume	Best response rate
		Duration of maintenance of a ≥35% reduction from Baseline in spleen volume

2 Statistical methods

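### Loss of the ≥35% spleen volume reduction does not end the 'duration of maintenance of a ≥35% reduction', so the curve shows time from first response to protocol-defined progression or death

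*SAP*

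**What the plan says.** SAP Table 1-1 lists the secondary endpoint as "Duration of maintenance of a ≥35% reduction from Baseline in spleen volume", under the objective of evaluating duration of response. SAP 2.7 starts the clock at the first volume that is at least 35% below Baseline. For the stop it says "the end date of the response duration is defined as the earliest of the following", and lists death, a ≥25% increase in spleen volume over Baseline, splenic irradiation, leukemic transformation and splenectomy. A second list in SAP 2.7, giving the date to use for each event, covers the same events.

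Protocol 10.5.4 is equivalent. It ends the duration at death or "Any protocol-defined event of disease progression (see Section 6.2.4.1". Protocol 6.2.4.1 has one volume criterion, a ≥25% "increase in spleen volume by MRI compared to Baseline: the Investigator will be notified via the central reader". The others are irradiation, leukemic transformation and splenectomy.

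On censoring, SAP 2.7 states: "The censoring date is defined as the date of the last adequate assessment of spleen volume for patients with no event of disease progression". It adds: "Patients who had more than 1 consecutive missing spleen volume assessment will be censored at the last adequate assessment prior to the consecutive missing assessments". The analysis is a Kaplan-Meier estimate in responders only, and SAP 2.7 names it among the few secondary analyses to be repeated with updated data in the final report.

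**The concern.** The endpoint's name refers to holding a reduction of at least 35%. Protocol 2.2 chose that threshold because it regards it as clinically meaningful. The stopping rule never looks at the threshold again once it has been reached. A spleen that regrows to anywhere above 0.65 and below 1.25 times Baseline triggers nothing, even when none of the reduction remains.

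Regrowth short of progression is foreseen in the protocol: section 6.2.1.2 has a provision for palpable spleen length rising from the on-study nadir, with no reference to a 25% volume increase over Baseline. A reader of the final report is likely to take the curve as the time for which the reduction was held. If responders regrew without progressing, the report would answer the duration-of-response objective with a different quantity under that name.

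**Working it through.** The documents give no figure for this endpoint (no event count, target or power), so there is no stated result to reproduce. The check compares the volume thresholds and asks how far apart they are.

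**Inputs from the documents**
- Response: reduction ≥35%, so volume ≤ 0.65 x Baseline (SAP 2.7).
- Volume end event: increase ≥25%, so volume ≥ 1.25 x Baseline (SAP 2.7; Protocol 6.2.4.1).
- Scans: "at visits corresponding to Weeks 12, 24, 36, 48 and every 24 weeks thereafter" (Protocol 7.2.1.1). In Protocol Table 7-2 the row "MRI of abdomen (or CT") is marked only under scheduled treatment visits, not End of Treatment.
- 120 patients analysed (SAP 1); design response rate 0.35 and response rate of 41.9% in the cited placebo-controlled study (SAP 3).

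**How a responder is classified, by current volume, if no other listed event occurs**

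| Volume / Baseline | ≥35% reduction held? | Rule as written |
|---|---|---|
| ≤ 0.65 | yes | continues |
| > 0.65 and < 1.25 | no | continues, or censored at last adequate scan |
| ≥ 1.25 | no | event |

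The middle row is the fault. It includes a full return to Baseline (1.00).

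**Width of the gap.** Growth needed from the response threshold to the volume event: 1.25/0.65 − 1 = 0.923, or 92%.

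**Reach of the volume event.** Assume a responder at exactly 0.65 at Week 24 and constant proportional growth. The annual growth needed to reach 1.25 by Week W is exp[ln(1.25/0.65) x 52.18/(W − 24)] − 1:
- W = 96: 0.606 (61% per year)
- W = 144: 0.329 (33%)
- W = 192: 0.225 (23%)

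Slower regrowth gives no volume event by that scan, although the reduction has been lost. These weeks fall on the scan schedule, but the documents do not state the length of follow-up.

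**Weight of one patient.** Assume 120 x 0.35 = 42 responders, or 120 x 0.419 = 50.3 (taken as 50), with no censoring and no other event. Each responder who regrows into the middle band would lower the proportion shown as maintaining by 1/42 = 2.4 points or 1/50 = 2.0 points. The counts use Week 24 rates, whereas this analysis takes responders at any time, so the true number may be higher. This is the weight of one patient, not an estimate of bias.

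**Direction.** For each patient, the observed end or censoring date under the written rule is the same as, or later than, the date with loss added as an event. That does not fix the direction of the Kaplan-Meier median when there is censoring. Example: A loses the reduction at time 1 and has a listed event at 3; B is censored at 2; C is censored at 4.
- Written rule: two at risk at time 3, S = 1/2, median 3.
- Loss counted: three at risk at time 1, S = 2/3 from then on, median not reached.

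So duration is expected to be overstated if any responder regrows past 0.65, but the median need not move the same way.

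**The case against.** The strongest reply is that this is a disclosed, pre-specified choice. Protocol and SAP agree, and the SAP spells out every event, its date source and the splenectomy case. Ending a response at progression or death is a recognisable convention, and the body text often says duration of response. On this view only the heading is too narrow, and a footnote would be enough. It is true that nothing is hidden and that the documents do not conflict. But agreement does not make the rule measure what the endpoint is called, and a footnote alone would leave the named quantity unreported.

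A second reply concerns the alternative. Dosing is titrated, with increases, reductions and restarts under Protocol 6.2, so a spleen may cross 0.65 briefly and recover. A first-crossing rule would end maintenance permanently, and after Week 48 confirmation takes 24 weeks. This stands, and is the reason for a confirmed-loss sensitivity analysis. The added analyses would also be chosen after open-label Week 24 results, which must be disclosed.

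Third, the size is unknown, the endpoint is secondary, and Protocol 10.9 claims no power for secondary variables. All of that stands. RAP Module 3 Amendment 2, Protocol 10.6 and SAP 2.9, 2.10, 2.12 and 2.13 could not be seen, so a loss-of-response analysis may exist there. The final SAP nevertheless restates the duration rule in full, and section 2.7 contains no such analysis.

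**Conclusion.** The concern holds. Following the plan exactly reports time from first response to protocol-defined progression or death under the title of maintaining a ≥35% reduction. Confidence is high on this mismatch, which rests only on the text and the 92% gap between thresholds. No size is claimed for this trial: the effect depends on how many responders regrew to between 0.65 and 1.25 x Baseline, and is nil if none did. The growth rates and per-patient weights above rest on the assumptions stated with them. The primary analysis is untouched, but this should be corrected because the result is one of the few efficacy findings carried into the final report.

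**What to change.** 1. Keep the pre-specified analysis and its name, so that the Week 24 and final reports stay comparable. Add a title line or footnote stating that it measures time from first response to protocol-defined progression or death.
2. Report beside it a separately labelled Kaplan-Meier analysis, time to loss of the ≥35% reduction. It ends at the earliest of the first post-onset MRI or CT scan with <35% reduction from Baseline, or any event now listed. Apply the existing rule for consecutive missing scans unchanged.
3. Add a sensitivity analysis requiring the loss to be confirmed at the next scan. Date the loss at the first of the two scans; censor an unconfirmed loss on the final scan at that scan; count a listed event before the confirming scan at its own date.
4. State that scans are 12 weeks apart to Week 48 and 24 weeks apart afterwards, with none scheduled at End of Treatment, so loss between scans or after the last one is not seen.
5. Record the addition in SAP section 4, which now reports no change, as made after the Week 24 results. If an unseen document already holds such an analysis, a cross-reference and the footnote suffice.

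The cost is one derived variable, one Kaplan-Meier table, one sensitivity run, a footnote and a SAP entry. Volumes are already read centrally at each scheduled scan, so no new data are needed. The downside is a second duration figure, probably shorter, with disclosure that it was added late.

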Based on these data, in Study [CINC424A2202] as well as ongoing western phase 3 studies (Study [INCB-18424-351] and [CINC424A2352]), 15 mg BID will be the starting dose for all patients entering the study with a platelet count between $100,000/\mu$ L and $200,000/\mu$ L (inclusive), whereas 20 mg BID will be the starting dose for all patients entering the study with a platelet count >200,000/\muL. With this dosing scheme, patients with higher platelet counts will start at a dose more likely to result in robust spleen reduction, while patients with a lower platelet level will begin with a dose that appears to have a very low incidence of thrombocytopenia. An optional dose increase of 5 mg BID for inadequate efficacy will occur at Week 4, provided platelet counts and ANC levels are in a satisfactory range. Mandatory dose decreases for safety reasons will be dictated by platelet count and ANC levels. These dose increases and decreases are summarized in Section 6.2.

The pharmacokinetics of INC424 in Japanese healthy volunteers (preliminary results of Study [CINC424A1101]) was similar to those in healthy volunteers studied in Western trials ([INCB 18424-131], [INCB 18424-132], [INCB 18424-138]). This is consistent with the fact that the primary metabolic enzyme of INC424 is CYP3A4 and ethnic differences are not expected in this enzyme expression or activity. These results suggest that the pharmacokinetics in an Asian population will be similar to the western population.

3 Objectives and endpoints

Primary Objective

• To determine the efficacy of INC424 as assessed by reduction in spleen volume

[figure not shown]
Secondary Objectives

- To determine the safety and tolerability of INC424
- To evaluate the effects of INC424 on patient reported outcomes
- To evaluate the duration of response as assessed by reduction in spleen volume

Objectives and related endpoints are described in Table 3-1 below.

	Objective	Endpoint	Analysis			
Primary	To determine the efficacy of INC424 as assessed by reduction in spleen volume	 Proportion of patients achieving ≥35% reduction in spleen volume from Baseline to Week 24 as measured by MRI (or CT scan in applicable patients) 	Refer to Section 10.4			

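### SAP 2.7 lets a response start on any spleen volume measurement but counts the ≥25% volume-increase end event only on MRI, which biases duration of response upward for responders followed by CT

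*SAP*

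**What the plan says.** **Start of response.** SAP 2.7: "The start date of the duration is defined as the first spleen volume measurement that is" at least 35% below Baseline. No imaging method is named.

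**End of response by spleen growth.** SAP 2.7 names MRI three times. The event list has a ≥25% "increase in spleen volume by MRI compared to Baseline". The paragraph after it, on stopping study drug, repeats the MRI condition. The event-date list uses the date of a ≥"25% increase compared to Baseline measured by MRI". Protocol 10.5.4 takes its end events from protocol 6.2.4.1, which also has a ≥25% "increase in spleen volume by MRI compared to Baseline: the Investigator will be notified via the central reader".

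**Other end events.** Death, splenectomy, splenic irradiation and leukemic transformation carry no imaging condition.

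**CT.** Protocol 7.2.1.1: "CT scans may be performed if the patient is not a candidate for MRI", and "CT scans will be similarly processed by the same central laboratory as used for MRIs". Protocol 9.3.2 requires one method per patient throughout unless a new contraindication to MRI arises. SAP Table 1-1 and SAP section 3 name CT alongside MRI for the response endpoint.

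**Notification.** Protocol 7.2.1.1 has the central reader tell the investigator of a ≥25% increase and names no method.

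**Censoring.** SAP 2.7 censors patients without an event at the last adequate spleen volume, with no method named.

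**The concern.** The start and censoring rules accept any spleen volume, but the volume-based end rule accepts only MRI. A patient who cannot have MRI can therefore enter the duration analysis as a responder and be censored on CT scans, while growth seen on those scans does not end the response. The same applies to a patient who moves to CT during the study. An observed failure becomes a censored observation, and the censoring is informative because it is tied to the failure itself.

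The ≥25% increase is the only end event that uses the measure named in the objective, spleen volume. Duration of response is also one of the two efficacy analyses that SAP 2.7 repeats with updated data for the final report. The date rule is the line a programmer would code, and the SAP has no other rule for a ≥25% increase seen on CT.

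**Working it through.** The plan gives no figure for duration of response, so there is none to reproduce. The check compares the rules and then bounds the effect.

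**1. A CT-followed responder under the rules as written**

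| Step | Rule | Does a CT volume count? |
|---|---|---|
| Enter as responder | SAP 2.7, start date | Yes, no method named |
| Volume-increase event | SAP 2.7, event list and date list | No, MRI only |
| Death, splenectomy, irradiation, leukemic transformation | SAP 2.7 | Not dependent on imaging |
| Censoring | SAP 2.7, last adequate spleen volume | Yes, no method named |

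Two outcomes follow for a ≥25% increase on CT with no other event:
- If treatment stops after the notification, no imaging is scheduled at End of Treatment or Follow-up (protocol Table 7-2). The last adequate volume is then that same scan, so an event becomes a censoring on the same date.
- If treatment and scans continue, the patient stays in response until a later scan.

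**2. Patients exposed (assumed CT share)**

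The SAP introduction gives 120 patients and SAP section 3 an expected response rate of 0.35, so 120 × 0.35 = 42 responders; take 40. With an assumed 5-15% on CT, 40 × 0.05 = 2 and 40 × 0.15 = 6. These are exposed patients, not lost events.

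**3. Events lost**

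Assume exponential durations with a 24-month median, so λ = ln 2 / 24, and uniform censoring over 0-60 months. The share of responders with an event is 1 − (1 − e^(−60λ)) / (60λ) = 1 − (1 − 0.177) / 1.733 = 0.525. Assume 30-80% of events are volume increases. Lost events are then 2 × 0.525 × 0.3 = 0.3 up to 6 × 0.525 × 0.8 = 2.5.

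**4. Effect on the median**

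Let c be the CT share and s the share of end events that are volume increases. If the CT increase is censored at that scan, CT and MRI patients leave the risk set at the same rate. The observed hazard is then λ(1 − cs) and the estimated median is 24 / (1 − cs).

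| CT share c | Events lost, s = 0.3 to 0.8 | Estimated median (true 24 months) |
|---|---|---|
| 2% | 0.6-1.6% | 24.1-24.4 |
| 5% | 1.5-4.0% | 24.4-25.0 |
| 10% | 3.0-8.0% | 24.7-26.1 |
| 20% | 6.0-16.0% | 25.5-28.6 |

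A simulation of 400,000 patients per cell agrees to within 0.1 month.

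If CT patients instead stay under observation after the increase, the shift is a little larger. For c = 0.10 and s = 0.5, solve 0.9x² + 0.1x = 0.5 with x = e^(−λt/2). This gives x = 0.692 and t = 25.5 months, against 24 / 0.95 = 25.3.

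**The case against.** The best defence is that MRI is the protocol's shorthand for the scheduled volume scan. Protocol 7.2.1.1 schedules MRI for all patients before allowing CT. Protocol 7.1.2 asks for a verified Baseline MRI, and 6.2.1.2 asks for the visit's MRI before a dose increase. Table 7-1 shows that the scan meant is MRI or CT. Read as strictly as SAP 2.7 is read here, a CT patient would have no valid Baseline scan. The notification in 7.2.1.1 also names no method. This reading is plausible and may be what was intended. It does not settle the matter, because the SAP adds CT where it states the response endpoint and omits it throughout the end event, including the date rule.

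A reader might infer that CT patients cannot progress at all. The documents do not support that: death, splenectomy, splenic irradiation and leukemic transformation still end their response. Nor does such a patient necessarily gain response time, since the censoring date may be that of the scan showing the increase.

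The 30-80% assumption may also be generous. A responder at 65% of Baseline or less must reach 125%, which is growth by a factor of at least 1.25 / 0.65 = 1.92. Finally, the analysis is a descriptive Kaplan-Meier estimate with no test attached. These points limit the size of the problem; they do not remove the mismatch.

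**Conclusion.** The mismatch is real on the text of SAP 2.7. Followed literally, a ≥25% increase on CT is not an end event and, absent another event, becomes a censoring. The bias is towards longer duration.

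Its size cannot be fixed from the documents because the CT share is not stated. Under the assumptions above, the median shifts by 0.1-0.4 months at a 2% CT share, 0.7-2.1 months at 10% and up to 4.6 months at 20%. With few patients on CT it is probably small. A reader might conclude that the reported duration is materially inflated; nothing in the documents establishes that. The primary endpoint allows CT and is unaffected.

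**What to change.** - In the SAP 2.7 event list and event-date list, count a ≥25% increase from Baseline in the centrally read spleen volume, by MRI or by CT in patients for whom CT applies.
- State how a change of method is handled, in particular a CT volume compared with an MRI Baseline.
- Ask the sponsor to reconcile the MRI-only progression and discontinuation wording, in protocol 6.2.4.1 and in the SAP 2.7 paragraph between the two lists, with the notification in protocol 7.2.1.1. Which discontinuation rule applies is for the sponsor to state; this point does not propose one.
- If the revised analysis rule departs from protocol 10.5.4, record it in SAP section 4, which now lists no changes.

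The cost is a few words and a small programming change. No new data are needed, since CT volumes already go through the same central laboratory. The downside is that the duration estimate may come out slightly shorter.

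### SAP 2.7 counts a responder's death as the end of response, but its censoring sentence, read literally, also censors a responder who dies without progression

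*SAP*

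**What the plan says.** **SAP 2.7, opening event list.** For patients with at least one reduction of 35% or more, "the end date of the response duration is defined as the earliest of the following": death, a spleen volume increase of at least 25% over Baseline, splenic irradiation, leukemic transformation, splenectomy. Death comes first and carries no condition.

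**SAP 2.7, restated date list.** A few lines later the end date "will be defined as the earliest date for one of the following for patient with any event of disease progression". Date of death is again the first bullet, but now under a heading limited to patients with progression.

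**SAP 2.7, censoring.** "The censoring date is defined as the date of the last adequate assessment of spleen volume for patients with no event of disease progression". The next sentence censors patients with more than one consecutive missing spleen assessment at the last adequate assessment before the gap, "regardless of the occurrence of a subsequent death or any event of disease progression".

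**Protocol 6.2.4.1.** "The following events are considered disease progression": the volume increase, splenic irradiation, leukemic transformation and splenectomy. Death is absent.

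**Protocol 10.5.4.** Death and protocol-defined progression are two separate end-event bullets. The censoring sentence is "Censoring date is defined as the date of the last adequate assessment of the spleen volume", with no condition about progression.

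**SAP 4** declares no change to the protocol-specified analyses.

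**The concern.** The censoring condition in the SAP turns on disease progression alone. Under the protocol's definition, a responder who dies with none of the four progression events is a patient with no event of disease progression, so the sentence sends that patient to the last adequate scan as censored. The event list gives the same patient an event on the date of death.

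The choice affects the estimate. Death ends a response. Censoring it makes the Kaplan-Meier method treat the dead patient as if they had the same future chance of staying in response as those still followed, which raises the curve. Duration of response is one of the few efficacy analyses to be repeated for the final report, and treatment may continue until commercial access, so some responders may die during follow-up.

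**Working it through.** The plan states no expected duration, event count or death rate for responders, so there is no figure to reproduce. The check is mainly textual.

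**1. Apply each rule to a responder who dies with no progression event and no missed scans.**

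| Rule | Result |
|---|---|
| SAP 2.7, opening list | Event, date of death |
| SAP 2.7, restated list, heading read with the Protocol 6.2.4.1 definition | Not covered |
| SAP 2.7, restated list, progression read as any listed event | Event, date of death |
| SAP 2.7, censoring sentence, read with the Protocol 6.2.4.1 definition | Censored, last adequate scan |
| Protocol 10.5.4, end events | Event, date of death |

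**2. Does the text say that progression includes death?** No. Protocol 6.2.4.1 omits it, Protocol 10.5.4 lists the two separately, and the SAP's missed-assessment sentence names them as alternatives.

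**3. Where does the condition come from?** It is in the SAP's censoring sentence and not in the protocol's. SAP 4 does not list it as a change.

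**4. Direction.** With n patients at risk, a death counted as an event multiplies the Kaplan-Meier estimate by (1 - 1/n). Counted as censored, it multiplies by 1. In principle, moving the censoring back to the last scan can lower the curve slightly if another patient has an off-schedule event in the gap. This does not alter the overall direction.

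**5. Size, as illustration only.** With constant yearly rates p for progression and d for death without progression, the share still in response at t years is exp(-(p + d)t) with death as an event and exp(-pt) with death censored. All rates are assumptions. At 96 weeks from the start of response, t = 96/52 = 1.846:

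- p = 0.10, d = 0.03: exp(-0.240) = 0.787 against exp(-0.185) = 0.831, a gap of about 4 points.
- p = 0.15, d = 0.20: exp(-0.646) = 0.524 against exp(-0.277) = 0.758, a gap of about 23 points.

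A simulation agrees. It used 400 trials of 50 responders per scenario, the protocol's MRI schedule with response starting at Week 12, progression detected at the next scan, dropout of 0.10 per year and follow-up to 156 weeks. Times are weeks since response began.

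| p, d per year | Week 48: death as event / censored | Week 96: death as event / censored |
|---|---|---|
| 0.10, 0.03 | 0.905 / 0.930 | 0.802 / 0.848 |
| 0.10, 0.08 | 0.868 / 0.933 | 0.735 / 0.851 |
| 0.15, 0.10 | 0.820 / 0.904 | 0.645 / 0.787 |
| 0.25, 0.10 | 0.766 / 0.841 | 0.555 / 0.670 |
| 0.25, 0.15 | 0.729 / 0.843 | 0.501 / 0.669 |
| 0.15, 0.20 | 0.741 / 0.900 | 0.540 / 0.784 |

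The censored version was never lower at any time point checked. The average gap ran from 2.5 to 16 points at week 48 and from about 5 to 24 points at week 96. The share of responders dying without progression, which drives these gaps, was 7% to 34% by assumption. The missed-assessment rule was not modelled.

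**The case against.** The strongest reply is that the SAP's intent is clear. Death is in both of its event lists and in Protocol 10.5.4, and SAP 4 declares no departure from the protocol. If the heading "for patient with any event of disease progression" covered only the four protocol events, the date-of-death bullet beneath it would do nothing: the rule takes the earliest date, and in a patient who progressed, death cannot come before progression. The bullet has effect only if the phrase is shorthand for any listed event, death included. On that reading the conflict disappears.

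This stands as evidence of intent. It also disposes of a stronger reading that a reader might infer, namely that the restated list selects censoring or that the plan is to censor deaths. A programmer working from that list would find date of death at the top. Nor do the documents show that deaths were censored in the Week 24 report: its methodology is in a separate analysis plan that is not available here.

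The reply does not repair the censoring sentence. The SAP never states the shorthand, and its next sentence uses the two terms as distinct.

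A reader might also try to size the bias from the median survivals of 48 and 27 months in Protocol 1.1. Those describe risk groups in a cited prognostic study, not treated spleen responders, and they do not give the share of deaths that occur on study without progression. The affected group is narrowed further: deaths after more than one consecutive missed scan are censored by explicit rule, the visit schedule has no MRI at End of Treatment or Follow-up, and the last planned assessment is 30 days after the last dose (Protocol 4.3).

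**Conclusion.** The point holds as a drafting conflict. For a responder who dies without progression, SAP 2.7 supplies both an event date and a censoring date, and does not say which prevails. The lists and the protocol indicate that death was meant to be an event. The censoring sentence taken literally would censor it and bias the Kaplan-Meier estimate upward.

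Only the direction is established. The size depends on how many responders die without progression before the missed-assessment rule applies, and the documents do not give that. The illustrative gaps rest wholly on assumed rates. The estimate is secondary and single-arm, and the primary Week 24 test is untouched, so this is a minor correction.

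**What to change.** Make two wording changes in SAP 2.7:

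- Censoring sentence: apply it to *patients with neither death nor any event of disease progression*.
- Heading of the restated date list: *for patients who died or had any event of disease progression*.

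The missed-assessment rule can stay as it is. The edits bring the SAP back into line with Protocol 10.5.4 and need no new data and no change in sample size. The only downside is that the estimate may be slightly less favourable than under the literal censoring rule.
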